CE	Conformité Européenne
CTCM	Clinical Trial Centre Maastricht
CV	Curriculum Vitae
DSMB	Data Safety Monitoring Board
EU	European Union
EudraCT	European drug regulatory affairs Clinical Trials
GCP	Good Clinical Practice
GDPR	General Data Protection Regulation; in Dutch: Algemene Verordening Gegevensbescherming (AVG)
IASP	International Association for the Study of Pain
IB	Investigator's Brochure
IC	Informed Consent
IMP	Investigational Medicinal Product
IMPD	Investigational Medicinal Product Dossier
LMWH	Low Molecular Weight Heparin
METC	Medical research ethics committee (MREC); in Dutch: medisch-ethische toetsingscommissie (METC)
NRS	Numeric Rating Scale
PCS	Pain Catastrophizing Scale

RCT	Randomized Controlled Trial
(S)AE	(Serious) Adverse Event
SPC	Summary of Product Characteristics; in Dutch: officiële productinformatie IB1-tekst
STAI	State-Trait Anxiety Inventory
Sponsor	The sponsor is the party that commissions the organisation or performance of the research, for example a pharmaceutical company, academic hospital, scientific organisation or investigator. A party that provides funding for a study but does not commission it is not regarded as the sponsor, but referred to as a subsidising party.
SUSAR	Suspected Unexpected Serious Adverse Reaction
UAVG	Dutch Act on Implementation of the General Data Protection Regulation; in Dutch: Uitvoeringswet AVG
VR	Virtual Reality
WMO	Medical Research Involving Human Subjects Act; in Dutch: Wet Medisch-wetenschappelijk Onderzoek met Mensen

1. SUMMARY

Rationale: Lack of postoperative acute pain management is associated with increased morbidity, longer recovery time, more opioid use and subsequently increased health care costs. There is increasing evidence virtual reality (VR) is effective in the reduction of acute pain. Alternative methods to reduce postoperative pain and multimodal analgesia are necessary for acute postoperative pain management and to reduce opioid use and their adverse effects.

Objective: The aim of this study is to explore the effect of VR on pain in the immediate postoperative period after elective gynecological surgery.

Secondary objectives are evaluating pre-and postoperative anxiety, pain catastrophizing, analgesic use, length of hospital stay between both groups and to explore tolerability, feasibility and satisfaction of VR use.

Study design: The study concerns a non-blinded, single centre, randomised controlled trial.

Study population: Eligible women fulfill the inclusion criteria and receive elective gynecological surgery under spinal anesthesia in the Zuyderland Medical Centre location Heerlen.

Intervention: The study population will be randomly divided into the intervention group (VR-group) or the standard care- group. The intervention group can choose for an immersive guided relaxation VR experience or an interactive VR experience during the pre- and postoperative period additional to the usual standard care. The participants randomised to the standard care- group will receive only the usual standard care pre-and postoperative.

Main study parameters: The primary outcome is postoperative pain measured on a numeric rating scale (NRS). A total of 30 patients have to be included in each group. This means that a total of 60 women will have to be included in the study.

Nature and extent of the burden and risks associated with participation, benefit and group relatedness:

The study population experiences a small medical risk when participating to this study. They can experience side-effects of VR for example dizziness or nausea and in rare cases epileptic insults.

Participants of the study have to fill in a questionnaire before randomization and pre-and postoperative score of pain and anxiety on a zero to ten score scale.

2. INTRODUCTION AND RATIONALE

“An unpleasant sensory and emotional experience associated with actual or potential tissue damage, or described in terms of such damage”, this is the definition of pain according to the International Association for the Study of Pain (IASP) [1]. Severe post-operative pain is experienced by approximately 50-80% of the patients [2, 3].

Lack of postoperative acute pain management is associated with increased morbidity, longer recovery time, more opioid use and subsequently increased health care costs [2, 4, 5]. Postoperative pain can cause a higher morbidity, because of cardiovascular, pulmonic and gastro-intestinal problems [4, 5].

Besides, surgery and acute pain are both independent risk factors for the development of chronic pain [4, 6]. The reduction of acute pain and therefore managing postoperative pain may contribute to the prevention of chronic pain [6].

In general, nowadays, medication is the treatment of choice for acute pain and mainly opioid analgesics are used for pain relief [7]. Worldwide this contributes to excessive drug dependence and opioid abuse. Opioid use comes with several negative side effects, for example a potential delay in recovery and an increased risk of permanent disability [8].

Nowadays, new methods related to pain management are developed. For example, Virtual reality (VR) is an upcoming technology used within healthcare. It is thought that the perception of pain is related to the amount of attention that is given to pain stimuli [9]. The theory behind the working mechanism of VR to reduce pain is that VR acts as a distraction to limit the user’s processing of nociceptive stimuli, by stimulating the visual cortex in the brain [10]. In 2000, Hoffman published the first preliminary evidence for the beneficial effect of VR in reducing pain in a burn care unit [11]. They also showed a trend to experience less anxiety during VR use. In the next upcoming years, a growing body of research was done to explore the effects of VR.

A recent systematic review and meta-analysis showed VR to be an effective treatment for reducing acute pain [8]. Next to being effective in reducing pain, it is also a proven useful tool in reducing preoperative anxiety [12, 13]. VR can be used as a safe, non-invasive, analgesic method, without risks of drug addiction and minimum side effects [14, 15].

In this study, we want to explore the effect of VR on postoperative pain in patients undergoing elective gynecological surgery as a serious alternative for pain medication. We hypothesize VR will reduce post-operative pain and consequently postoperative opioid use and anxiety reduction.

3. OBJECTIVES

The aim of this study is to determine whether VR used in the immediate postoperative period after gynecological surgery will decrease pain scores.

Primary Outcome measure: reduction in postoperative pain score (NRS, numeric rating scale)

Secondary Outcome measures:

- Pre-operative anxiety (State-Trait Anxiety Inventory (STAI)-6 questionnaire)
- Pain catastrophizing (Pain Catastrophizing Scale questionnaire)
- Difference in anxiety scores pre-and post VR intervention (NRS)
- Analgesic use (daily use of paracetamol, NSAIDs, opioids)
- Length of hospital stay
- Tolerability, feasibility and satisfaction of VR use (questionnaire)
- Preoperative pain score (NRS)

4. STUDY DESIGN

The design of this study is a single centre, randomised controlled trial (RCT). Eligible patients will be randomised to either the VR- group and receive additional VR during the pre- and postoperative period or undergo standard pre- and postoperative management (standard care- group).

5. STUDY POPULATION

5.1 Population (base)

Patients who fulfill the inclusion criteria and receive elective gynecological surgery under spinal anesthesia in the Zuyderland Medical Centre.

5.2 Inclusion criteria

- Written and orally given informed consent
- 18 years and older
- Native Dutch speaker
- Indication for elective gynecological surgery under spinal anesthesia
- No contra-indication to spinal anesthesia:
 - Use of coumarines
 - Use of low molecular weight heparin (LMWH) in a therapeutic dosage
 - Use of LMWH in a prophylactic dosage used < 10 hours before surgery
 - Thrombocytes < 80x 10⁹/L
 - Use of thrombocytes aggregation inhibitors or increased risk of bleeding
 - Coagulation disorder
 - Allergy or hypersensitivity to anesthetics
 - Spinal problem

5.3 Exclusion criteria

- Chronic pain patients; defined as 'persistent or recurrent pain lasting longer than 3 months' [16]. The pain is not due to the gynecological problem.
- Chronical use of pain medication (opioids)
- History of prior opioid use defined as use within 8 to 90 days prior to the surgical procedure
- Alcohol or drug abuse
- Known car sickness
- Epileptic insults in previous history
- Psychotically seizures in previous history
- Claustrophobic
- Blindness
- History of mental illness

5.4 Sample size calculation

We are planning a study of independent cases and controls with 1 control(s) per case.

To be able to make an adequate sample size calculation the VR was set as the reference test, standard care will be compared to this procedures. Our hypothesis is that VR (intervention) will significantly improve the mean NRS for pain after surgery with 15 mm with a standard deviation of 20mm.

On the assumption of an effect of 15 mm we would need 26 patients per group; 30 taking into account loss of follow-up. Thus 60 patients need to be included. With this sample size we are able to achieve a power of 0.8. The Type I error probability associated with this test of this null hypothesis is 0.05.

We changed the sample size collection in consultation with the Orthopedic Department of the Zuyderland Medical Centre. They are planning to start with a comparable study. We strive for comparable studies, to if possible, eventually are able to perform collective analyses.

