9.2 Randomisation, blinding and treatment allocation

After receiving written informed consent, randomisation will be by the Datamanagement randomisation programme of 'Bureau Wetenschappelijk Onderzoek' Zuyderland Medical Centre. Randomisation will be 1:1 for intervention and the standard care- group. The study will be an open label, non-blinded study.

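### The 26 evaluable patients per group in section 5.4 do not give the stated 80% power: a two-sided t-test has about 76% at 26 and needs 29.

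*Combined protocol and SAP*

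**What the plan says.** Section 5.4 (Sample size calculation) describes two independent groups of equal size: "We are planning a study of independent cases and controls with 1 control(s) per case". Section 9.2 confirms the ratio: "Randomisation will be 1:1 for intervention and the standard care- group". The target is that VR "will significantly improve the mean NRS for pain after surgery with 15 mm with a standard deviation of 20mm". The error rate is given as: "The Type I error probability associated with this test of this null hypothesis is 0.05".

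From these inputs section 5.4 concludes: "On the assumption of an effect of 15 mm we would need 26 patients per group; 30 taking into account loss of follow-up". It then gives a total of 60 and adds: "With this sample size we are able to achieve a power of 0.8". The Summary (section 1) repeats the enrolment target: "A total of 30 patients have to be included in each group".

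Section 5.4 does not state whether the test is one- or two-sided, which test was used, what loss rate was assumed, or any gain from covariates or repeated measurements. Section 11 names the independent-samples t-test for normally distributed continuous variables, and section 11.1 names a linear mixed model for the primary outcome.

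**The concern.** A standardised difference of 0.75 with 80% power at a two-sided 5% level usually calls for 28 or 29 patients per group, so 26 looked too low. The gap matters because section 5.4 treats 26 as the number needed and the four extra per group as cover for losses. If 26 is too few, most of that cover is already needed to reach the stated power.

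This is the trial's only justification of its size. Section 5.4 also says the sample size was aligned with a comparable study planned by another department, with joint analysis in view, so the error could carry over into a second design.

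**Working it through.** **Inputs.** From section 5.4: difference 15 mm, SD 20 mm, alpha 0.05, power 0.80, two independent groups of equal size. Section 9.2 confirms 1:1. Two-sided testing is an assumption, so one-sided results are shown as well.

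**Step 1: standardised difference.** d = 15/20 = 0.75.

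**Step 2: try to reproduce 26.**

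- Two-sided, normal approximation: n = 2 × (1.960 + 0.842)² / 0.75² = 27.9, so 28 per group.
- Two-sided t-test (noncentral t): n = 28.9, so 29 per group.
- One-sided, normal approximation: n = 2 × (1.645 + 0.842)² / 0.75² = 22.0, so 22 per group.
- One-sided t-test: n = 22.7, so 23 per group.
- Paired or one-sample t-test (not this design): 16.

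None of these gives 26. With a two-sided t-test, 26 per group would follow from a difference of about 16 mm with SD 20 mm (n = 25.5), or from an SD of about 18.9 mm with a difference of 15 mm (n = 25.9). Neither is the printed input, and the document does not show how 26 was obtained.

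**Step 3: power at the sizes that matter.** For the normal approximation at 26 per group, d × √(n/2) = 0.75 × √13 = 2.704. Then 2.704 − 1.960 = 0.744, and Φ(0.744) = 77.2%. The t-test figure uses the same noncentrality of 2.704 on 50 degrees of freedom.

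| Evaluable per group | Two-sided t | Two-sided normal | One-sided t |
|---|---|---|---|
| 26 | 75.6% | 77.2% | 84.7% |
| 28 | 78.7% | 80.1% | 87.0% |
| 29 | 80.1% | 81.5% | 88.0% |
| 30 | 81.5% | 82.8% | 89.0% |

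With a two-sided t-test at 26 per group, the type II error is 100% − 75.6% = 24.4%, and the difference detectable with 80% power is 15.8 mm instead of 15 mm.

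**Step 4: the loss allowance.** Going from 30 to 26 is a loss of 4/30 = 13.3% per group. The t-test needs 29, so 30 − 29 = 1 patient per group (3.3%) can be lost before power falls below 80%. By the normal approximation it is 30 − 28 = 2. To keep 29 evaluable at the implied loss, enrolment would be 29 / (26/30) = 33.5, so 34 per group or 68 in total. No loss rate is stated. An assumed 10% gives 33 per group and an assumed 15% gives 35.

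**Step 5: units.** Section 5.4 works in millimetres, but section 6.1 has pain scored from 0 to 10. Taking 10 mm as 1 point, the inputs are 1.5 points and SD 2.0. Then d is still 0.75 and every figure above stands. The problem with the units is readability, not arithmetic.

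**The case against.** Four points can be made for the plan.

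1. **Sidedness is not stated and the hypothesis is directional.** With a one-sided 5% test, 26 per group would have 84.7% power. This is correct, and it makes the 76% conditional. It does not rescue the calculation, because a one-sided test needs only 23.

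2. **The power sentence follows the sentence about 60 patients.** Read that way, 30 per group gives 81.5% and the statement is true. The wording allows this reading. But the previous sentence calls 26 the number needed and 30 the number after allowing for loss. If 30 evaluable patients supply the power, the allowance for loss disappears. On a two-sided test, no reading makes both sentences right.

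3. **Losses may be small.** Both postoperative pain scores (T2 and T3) are taken on the recovery ward. Section 9.6 keeps patients who stop VR but agree to measurements, and section 11 allows imputation. Section 9.6 also allows replacement after complete withdrawal, although section 9.5 rules replacement out. Four losses per group may therefore never occur. Still, the plan itself budgets for 26, and the power it states should hold there.

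4. **The primary analysis is a mixed model, not a t-test.** Adjustment for a baseline covariate could recover the shortfall: at 26 per group, power would be 79.4% if the covariate's correlation with the outcome were 0.3, and 82.5% if it were 0.4. These correlations are assumed, and section 5.4 gives none. Nor is a gain guaranteed. Suppose the model averages T2 and T3 and there is no effect at T2, which is measured before the postoperative VR session. The averaged effect is then 7.5 mm, and power at 26 per group is 33.4% with an assumed correlation of 0.5. The model cannot be the source of 26.

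What stands is that 75.6% is the power of an unadjusted two-sided t-test at the planned loss, and that the shortfall is modest.

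**Conclusion.** The concern holds. The inputs in section 5.4 do not produce 26 per group under any standard calculation. For a two-sided two-sample t-test at 0.05, the plan needs 29 evaluable per group (28 by the normal approximation). At the 26 it plans for, power is 4.4 percentage points below the stated 80% (2.8 points by the normal approximation). Enrolling 60 reaches 80% only if at most one patient per group is lost (two by the normal approximation).

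The conclusion rests on two-sided testing and on no variance reduction from covariates, since the plan states none. Under a one-sided test power would be adequate, but 26 would still be the wrong answer. The error does not by itself make 60 patients an unreasonable number. It makes the printed justification incorrect, and it should be corrected because any reader can check it from the stated inputs.

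**What to change.** Restate section 5.4, keeping the total of 60. Suggested content:

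> For a difference of 1.5 points on the 0–10 NRS with SD 2.0, a two-sided two-sample t-test at 0.05 needs 29 evaluable patients per group for 80% power. We will randomise 60 patients (30 per group). Power is 81.5% with no loss and 75.6% if 26 per group are evaluable.

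Also:

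- State the assumed loss rate and make sections 9.5 and 9.6 agree on replacement, since that decides how many evaluable patients can be expected.
- Confirm that 10 mm is meant as 1 NRS point.
- If a gain from baseline adjustment is to be relied on, pre-specify the adjustment and the time point, and state the assumed correlation with its source.
- Pass the corrected figure to the department planning the comparable study.

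The cost is wording only: no extra patients and no change in conduct. The stated power becomes slightly less favourable. If the sponsor prefers to hold 80% at the implied 13.3% loss without relying on adjustment, the price is 34 per group, or 68 − 60 = 8 more patients.

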6. TREATMENT OF SUBJECTS

6.1 Investigational product/treatment

The study population will be randomly divided into the intervention group (VR-group) or the standard care-group.

Intervention group (VR-group):

The participants randomised into this group can choose for an immersive guided relaxation VR experience or an interactive VR experience. We will register which option the patients choose. The options are explained in paragraph 9.3. Pre-operatively when arriving at the pre-operative anesthetic room, the level of anxiety and pain is scored using the numeric rating scale (NRS) (T1a). After this, the VR- group will receive their VR experience of own choice on the pre-operative anesthetic room during 10-15 minutes. Directly after this VR intervention, the level of anxiety and pain is scored from 0-10 (T1b).

Direct postoperatively after arriving on the recovery ward, NRS score and level of anxiety from 0-10 will be scored by the participant (T2). Subsequently, the VR-group will receive the VR experience of own choice during 10 minutes. Before leaving the recovery ward, NRS score and level of anxiety from 0-10 will be measured (T3). Depending on the duration of stay on the recovery ward, an extra VR intervention will be given. If the patient stays for less than 3 hours, there will only be one VR intervention. If this is longer than 3 hours, there will be two interventions. The VR intervention is additional to the standard postoperative care management, the standard pain protocol is explained below.

The VR-intervention will be given using the Oculus Go Virtual Reality glasses with touchpad.

Standard pre-and postoperative management (standard care- group):

The participants randomized into the standard care- group will receive the usual standard pre-and postoperative management. Pre-operatively when arriving at the pre-operative anesthetic room, the level of anxiety and pain is scored from 0-10 (T1a). After 10-15 minutes the level of pain and anxiety is again scored from a scale from 0-10 (T1b). Direct postoperatively after arriving on the recovery ward, measurements like NRS score and level of anxiety from 0-10 will be scored by the participant (T2). Before leaving the recovery ward, NRS score and level of anxiety from 0-10 will be measured (T3).

Standard pain protocol:

1. Preoperative (arrival day-care unit) start with 1000mg paracetamol orally administered.
2. Postoperative Meloxicam 15mg orally administered, or when oral medication is not possible (due to nausea e.g.) than diclofenac supp 100mg or diclofenac i.v. 75mg.
3. On recovery ward, when necessary depending on pain score (NRS>4): dipidolor 2.5-5mg i.v. and 10-15mg i.m. after consulting the anesthesiologist.
4. Postoperative at home 4dd1000mg paracetamol will be continued, in combination with meloxicam 1dd15mg during 3 days. Also tramadol 50mg with a maximum of 4dd will be prescribed.

6.2 Use of co-intervention (if applicable)

Not applicable.

6.3 Escape medication (if applicable)

In case a patient will get a seizure because of using the VR glasses, the glasses will immediately be taken off. When the seizure will not stop after 5 minutes, 10 mg midazolam nasal can be administered. This can be repeated once. If midazolam is not effective, the neurologist will be asked for consultation.

7. INVESTIGATIONAL PRODUCT

7.1 Name and description of investigational product(s)

Oculus Go Virtual Reality glasses and touchpad. The Oculus Go is easy to use and wireless. It provides lifelike experiences using clear images, to offer visual clarity.

The CE-numbers of the products are known. Virtual reality glasses: R-CMM-0C8-MH-A and controller: R-CRM-0C8-MI-A. Following the technical service of the Zuyderland Medical Centre, the Virtual Reality glasses will be used as a distraction, no additional quality marks are necessary to use the glasses in this study.

7.2 Summary of findings from non-clinical studies

VR can be safely used in different settings, for example in the educative sector, in the sector of architects, or in healthcare.

7.3 Summary of findings from clinical studies

Different hospitals in the Netherlands are already using the VR glasses. Until now, only dizziness and nausea have been reported, and no other side-effects have been reported. This will be explained in paragraph 7.4.

7.4 Summary of known and potential risks and benefits

The user of the VR glasses can possibly experience complaints of nausea and dizziness. This is called motion sickness, and the side-effects of VR are comparable to the symptoms of carsickness or seasickness. Motion sickness refers to symptoms that can occur during the experience of a virtual environment. The main cause is the conflict of the visual feeling and the physical feeling that you can experience of the virtual environment. When those complaints occur, the intervention can be stopped immediately. Next to dizziness and nausea, also the risk of getting an epileptic insult can occur by using VR, this occurs in 1:4000 healthy persons. When a patient is known with epileptic insults, this will be an exclusion criteria and it is not possible to join the study. The chance of injury in the face by turning of the head of the person using VR is very small. With the least risk of a possible harmful effect of the glasses, the VR intervention will be stopped.

7.5 Description and justification of route of administration and dosage

Patients will use the VR glasses as glasses, this is the only 'route of administration'.

7.6 Dosages, dosage modifications and method of administration

The VR glasses will be used as glasses. It is not used in dosages, but used in you can state that one 'dosage' of Virtual Reality matches with use of VR for 15 minutes.

